11.10 Schedule of Procedures and Observations

The schedule of procedures and observations for this study is summarized in **Appendix J**.

PROTOCOL TITLE: I 49217 - Phase 1 CDX-1401/ Poly-ICLC +Decitabine +Nivolumab in Patients with MDS or Low Blast Count AML

11.11 Correlative Studies

11.11.1 Blood Sample Collection

Blood samples will be collected via venipuncture (green tops) for analysis of molecular markers, NY- ESO-1 cellular immune response (T-cell), (ELISPOT and ICS) and assessment of T-Regulatory cell frequency (CD4+CD25+FOXP3+ regulatory T cells) and, cell differentiation by transcription factor distribution (T-bet, GATA-3, ROR γ) and, gold-top tubes will be used for analysis of antibody response (NY-ESO-1-ELISA).

- Blood will be collected at the following time points:
 - Baseline:
 - 4, 10 mL green-top (sodium heparin) tubes ([name] lab)
 - 2, 10 mL green-top (sodium heparin) tubes (Immune Analysis Facility)
 - 1, 3.5 mL gold-top tube (Immune Analysis Facility)
 - Day -14 (prior to Cycle 1 Day 1):
 - 4, 10 mL green-top (sodium heparin) tubes ([name] lab)
 - 2, 10 mL green-top (sodium heparin) tubes (Immune Analysis Facility)
 - 1, 3.5 mL gold-top tube (Immune Analysis Facility)
 - Cycles 1-4 (once weekly):
 - 4, 10 mL green-top (sodium heparin) tubes ([name] lab)
 - 2, 10 mL green-top (sodium heparin) tubes (Immune Analysis Facility)
 - Cycle 5 and onward until end of treatment (Day 1 and Day 15) and, end of treatment:
 - 4, 10 mL green-top (sodium heparin) tubes ([name] lab)
 - 2, 10 mL green-top (sodium heparin) tubes (Immune Analysis Facility)
 - 1, 3.5 mL gold-top tube (Immune Analysis Facility)

Note: If it is determined that there is an inadequate cell number for cryopreservation and immunomonitoring at any visit, sample acquisition may be repeated at the next scheduled blood draw.

11.11.2 Bone Marrow Sample Collection

Study Bone marrow samples for T-cell and methylation and gene expression studies: 4, 10 mL green-tops tubes (sodium heparin) to be obtained each time a bone marrow assessment is to be done.

- Bone marrow samples will be collected at the following time points:
 - Baseline
 - End of Cycle 1 (**Note:** At the end of Cycle 1, if a bone marrow aspirate is not able to be done, a bone marrow biopsy may be performed instead)

PROTOCOL TITLE: I 49217 - Phase 1 CDX-1401/ Poly-ICLC +Decitabine +Nivolumab in
Patients with MDS or Low Blast Count AML

- Day 1 Cycle 5 and, Day 1 of every 4th cycle thereafter (+/- 14 day window acceptable)
- End of treatment
- If bone marrow is unable to be collected at noted time point and clinically appropriate, a bone marrow samples should be performed next cycle to document disease status.
- If a bone marrow is unable to be collected due to dry tap, collect 4 additional, 10 mL green-tops tubes (sodium heparin) of peripheral blood

Blood and Bone Marrow Processing

Samples (blood and/or bone marrow) will be processed at each site (**Appendix G**). The cryovials are to be labeled with the clinical study number and patient study ID, collection date/study cycle and day and “Blood” or “Bone marrow.”

The cryovials will immediately be frozen in liquid nitrogen and stored until requested for batch mailing. Samples are to be batch shipped frozen, on dry ice to:

Roswell Park Cancer Institute
[name]
Attn: [name], I 49217 Samples
[name]
[name]
[name]
[contact] (lab) or,
[contact] (cell)
[contact]

For Network Sites: Follow directions above for sample collection and processing. The cryogenic tubes are to be labeled with the clinical study number and patient study ID, collection date/study cycle and day and, “Blood” or “Bone marrow”. The processed samples will immediately be frozen in liquid nitrogen and stored until requested for batch mailing. Samples are to be batch shipped frozen, on dry ice.

Frozen samples will be shipped via Fed Express Overnight on dry ice with delivery on Mon-Fri. NO SATURDAY DELIVERY. Do not ship on a Friday or the day before a holiday.

Note: All investigator or analyzing research laboratories housing research samples need to maintain current Temperature Logs and study-specific Sample Tracking and Shipping Logs. The Principal Investigator/Laboratory Manager must ensure that the stated lab(s) have a process in place to document the receipt/processing/storage/shipping of study-related samples/specimens. This is required for both observational and interventional clinical studies collecting clinical samples

Cellular and/or humoral immune response assays (see below) will be performed by the RPCI Immune Analysis Facility under the direction of [name]:

Roswell Park Cancer Institute
Immune Analysis Facility Shared Resource

PROTOCOL TITLE: I 49217 - Phase 1 CDX-1401/ Poly-ICLC +Decitabine +Nivolumab in Patients with MDS or Low Blast Count AML

[name]
[name]
[name]
[contact]

[contact]

11.11.3 Molecular (Epigenetic) Markers of Response

Assays of samples to determine if circulating cells demonstrate the expected changes in global and gene specific (NY-ESO-1) methylation, gene expression (NY-ESO-1) and protein expression (NY-ESO-1) responses will be performed in the [name] Laboratory at the RPCI, Buffalo, NY. Assessment of molecular response, by error corrected sequencing, to protocol therapy will be sent out to [name] at the National Institutes of Health.

These assays are in routine use in my laboratory (see Figure 1) and we anticipate no difficulties performing them. Myeloid cells will be enriched from whole blood using CD11b MicroBeads and the MACS® Column separation method (Miltenyi Biotec, Bergisch-Gladbach, Germany). DNA, RNA and protein will be extracted using QIAamp DNA/RNA/Protein Mini and QIAamp DNA Blood Maxi kits (Qiagen, Valencia, CA). Given that some patients with MDS have very low numbers of circulating cells, isolation of the myeloid compartment may limit sample quality, and thus if separation proves unsuccessful, we will isolate DNA, RNA and protein from whole blood instead as this method has also been validated in MDS patients receiving HMA therapy (51). We have successfully collected informative samples from other MDS patients in this manner without difficulty. Any samples that are not informative will be censored. At each time point NY-ESO-1 promoter methylation (by bisulfite pyrosequencing) and NY-ESO-1 mRNA (by RT-PCR) will be determined. Assessment of LINE-1 methylation (also by bisulfite pyrosequencing) will be done as a marker for changes in global methylation over the course of each cycle (4, 52). One sample per week will be assayed for NY-ESO-1 protein expression by Western Blot (maximum 16 per patient). These analyses will allow us to demonstrate changes in NY-ESO-1 over the course of the treatment cycle and correlate them with the immunological parameters described below

11.11.4 Immunological Markers of Response

Assays to determine whether vaccination with CDX-1401/poly ICLC in series with decitabine and nivolumab can induce NY-ESO-1 specific cellular and/or humoral immune responses will be performed by the Immune Analysis Facility. MDS is characterized by bone marrow hypercellularity in association with peripheral blood cytopenias, increased rates of infection and autoimmune phenomena (53-55). Despite overt cytopenias and the possibility that in MDS the immune system does not function normally, we and other authors have successfully induced antigen specific T-cells following neo-antigen vaccination in patients with MDS and endogenous humoral immunity has also been shown [(56, 57) and Srivastava P et al. Blood 2016;128: 4326]. Therefore, we anticipate that induction of NY-ESO-1-specific immune responses is feasible. We are eager to test if the addition of nivolumab to our prior backbone will result in substantial enhancement of such responses. Furthermore, since induction of interferon-gamma (IFN γ) producing CD4+ and CD8+ T-cells are associated with improved clinical outcome in ovarian cancer patients expressing NY-ESO-1, documentation of a sustained immunological response in

PROTOCOL TITLE: I 49217 - Phase 1 CDX-1401/ Poly-ICLC +Decitabine +Nivolumab in Patients with MDS or Low Blast Count AML

MDS is of significant potential clinical interest (58, 59). Two major potential mechanisms that could account for a failure to induce NY-ESO-1 specific T- and B-cell responses include APC dysfunction and the activity of Tregs.

11.11.5 Humoral Immunity

We will test patients treated on the study for the production of NY-ESO-1 specific antibodies. Since documentation of a humoral immune response is associated with the activity of cancer vaccines in solid tumors such a response would be of interest (60). Induction of NY-ESO-1 specific antibody will be tested serially at baseline, at the end of cycle 4 and every 4th-8th cycle of decitabine therapy. An ELISA assay will be used to measure anti-NY-ESO-1 antibody titers (61). Comparison of antibody titers over the course of therapy will allow us to determine the humoral immunogenicity of this combination.

Specific antibody against NY-ESO-1 will be measured by ELISA [(62) for methodology]. Assays will be performed by the Roswell Park Cancer Center Immune Analysis Facility.

11.11.6 Cellular Immunity

The ability of the vaccine alone and in combination with decitabine and nivolumab to induce NY-ESO-1 specific, IFN γ secreting CD4+ and CD8+ T-cells will be measured. Samples will be obtained at baseline, and serially as described above. NY-ESO1 specific T-cell responses will be assessed using an in vitro T cell pre-sensitization, a method for the amplification of broadly HLA reactive NY-ESO-1-specific CD8+ and CD4+ T cells (51). Positive control stimulation with CEFT peptide (cytomegalovirus, Epstein-Barr virus, flu viruses (collectively) and tetanus toxoid (T) epitopes) is set up in parallel. Ten to 14 days after pre-sensitization, the frequency and the response of NY-ESO-1 specific cells will be analyzed by intracellular cytokine staining and ELISPOT assays for IFN γ as previously described (63). Comparison of the frequency of NY-ESO-1-specific T cells at baseline with samples derived serially will allow us to determine the immunogenicity of our combination. In addition to the peripheral blood studies described here, pre-treatment and off study bone marrow samples will be assessed for the presence of NY-ESO-1 specific T-cells as above and analyzed by flow cytometry for frequency of CD4+, CD8+, FOXP3+ and CD19+ cells.

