7 STUDY TIMELINES

- During the 3+3 component, accrual will be suspended until the three patients in each cohort have completed the DLT window (6 weeks after the last patient has begun therapy).
- Patients will be enrolled and treated on study for as long as they are deriving clinical benefit. Treatment on study has no specified end time.
 - Median progression free survival for patients with MDS receiving hypomethylating agents on clinical trials is between 18 and 24 months.
 - This study is therefore likely to enroll all 18 patients within 2 years and all patients are likely to have completed the study within 7 years of study opening.
- An interim analysis of correlative studies will be performed after every 3 patients have been enrolled and treated on the study for at least 5 months or come off treatment, whichever comes first.
- Given the long half-life for nivolumab and the known risk of late presenting adverse events, patients enrolled and treated on study will be followed for AEs for 180 days after the last dose of nivolumab.
- Patients will stay on study for 5 years after the last patient has been enrolled or until disease progression, whichever occurs first.

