8.2 Secondary Endpoint(s)

- To evaluate the induction of NY-ESO-1 specific cellular and humoral immunity by determination of NY-ESO-1 specific antibody, and NY-ESO-1 specific T-cell responses following standard treatment with decitabine in conjunction with immune sensitization with CDX-1401/poly-ICLC and nivolumab.
 - To evaluate the Immune cell profile in the peripheral blood and bone marrow following combination therapy using mass cytometry
 - To determine the impact of combination treatment on peripheral blood and bone marrow cells from patients treated in this manner on NY-ESO-1 target gene expression, NY-ESO-1 protein expression, NY-ESO-1 promoter methylation, and global DNA methylation.

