	≥2 out of 6	Stop the study.

Patients may elect to discontinue nivolumab and/or vaccine after Cycle 8 and remain on study receiving single agent decitabine to allow collection of the secondary and exploratory endpoints as described above.

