- 2 Performed 30 days, 60 days, 90 days, and 180 days (± 3 days) following last dose of study drug (last immunization with CDX-1401/poly ICLC/nivolumab). Assessment may be collected via telephone if the patient elects to come off study and is no longer coming to clinic.
- 3 Height collected at baseline only.
- 4 Physical examination on day -14 and day 1 of each cycle (or up to 3 days prior to the beginning of a cycle) and at end of treatment
- 5 Vital signs including temperature, heart rate, oxygen saturation, respiratory rate, body weight and blood pressure prior to CDX-1401/poly ICLC dosing on day -14 and day 15 of each cycle (cycles 1-4) or day 1 of each 4th cycle (cycles 5+) and prior to decitabine dosing on day 1 of each cycle
- 6 CBC with manual differential

PROTOCOL TITLE: I 49217 - Phase 1 CDX-1401/ Poly-ICLC +Decitabine +Nivolumab in
Patients with MDS or Low Blast Count AML

- 7 Once per week each cycle during cycles 1-4, from cycles 5 onward on Day 1 and as clinically indicated. Used to assess hematologic improvement per modified International Working Group criteria for MDS on Day 1 every cycle 1.
- 8 CMP, LDH, uric acid, amylase and, lipase. Once per week each cycle during cycles 1-4 and, on Day 1 from cycle 5 and onward and, as clinically indicated.
- 9 Bone Marrow Aspirate and Biopsy, Flow Cytometry, Conventional Cytogenetics+/- FISH as appropriate. At the end of cycle 1 a Bone Marrow aspirate is to be done purely for collection of correlative specimens, unless the patient has demonstrated sufficient clinical response to warrant disease assessment at the discretion of the treating physician. **Note:** At the end of Cycle 1, if a bone marrow aspirate is not able to be done, a bone marrow biopsy may be performed instead. Thereafter a complete bone marrow assessment to be done every 4th cycle (per standard of care) for response assessment. If bone marrow is unable to be obtained due to dry tap, collected 4 additional green top tubes of peripheral blood.
- 10 **CDX-1401/poly-ICLC** administered on day -14 of cycle 1 and then *day 15 of every cycle for the first 4 cycles.*
NOTE: After Cycle 4: to be given on *day 1 of every 4th cycle as a booster (i.e. on day 1 of cycles 8, 12, 16, 20, 24).*
10a: Decitabine administered on days 1-5 of each cycle.
10b: Nivolumab administered every 2 weeks on days 1 and 15 of each cycle for the first 4 cycles.
Note: After Cycle 4: to be given on day 1 of every cycle 5 and above

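### The marrow NY-ESO-1 T-cell and lymphocyte flow assays have no designated on-treatment sample, although on-treatment marrow is already collected for T-cell studies

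*Combined protocol and SAP*

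**What the plan says.** Section 11.11.6 deals first with blood, which is sampled repeatedly: "Comparison of the frequency of NY-ESO-1-specific T cells at baseline with samples derived serially will allow us to determine the immunogenicity". It then adds marrow, where "pre-treatment and off study bone marrow samples will be assessed for the presence of NY-ESO-1 specific T-cells". The marrow flow cytometry for CD4+, CD8+, FOXP3+ and CD19+ cells is attached to the same two samples.

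Section 11.11.2 is broader. Under the label "Study Bone marrow samples for T-cell and methylation and gene expression studies" it collects four 10 mL tubes at baseline, end of cycle 1, C5D1, every fourth cycle thereafter and end of treatment. Sections 11.6 and 11.7 repeat that purpose for the on-treatment collections. Appendix J says of the first of these: "At the end of cycle 1 a Bone Marrow aspirate is to be done purely for collection of correlative specimens".

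On timing, Section 7 sets no end to treatment and states: "Median progression free survival for patients with MDS receiving hypomethylating agents on clinical trials is between 18 and 24 months". Section 10.6 takes patients off study for transplant or a change of therapy at progression. Sections 10.1 and 12.1 add a delay of more than 6 weeks, toxicity, noncompliance, withdrawal and investigator decision. Section 9.1 adds: "Patients may elect to discontinue nivolumab and/or vaccine after Cycle 8 and remain on study receiving single agent decitabine".

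Sections 19.4 and 19.6 describe immune markers as measured at baseline and at set times while the patient is on treatment.

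**The concern.** Read as written, Section 11.11.6 gives the two marrow assays one post value per patient, taken when the patient leaves. That time depends on outcome: a patient who fails early gives an early sample, and one who does well gives a very late one. At progression, a low marrow T-cell count could mean that no response was induced, or that a response was induced and later lost. A sample taken only then cannot separate the two. In a patient who has been on decitabine alone for many cycles, the sample also says little about the combination, which is the subject of the secondary objective in Section 1.2.

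The other immune assays have on-treatment times. Blood T cells are compared serially, antibody is tested at the end of cycle 4 (Section 11.11.5), and antigen-presenting cell function is tested after 2 and 4 cycles (Section 11.11.7). The marrow T-cell and flow results could not be set beside any of them at a common time.

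**Working it through.** The plan states no sample size or power that depends on this point, so there is no figure to reproduce. The check sets the schedules side by side and does calendar arithmetic with 28-day cycles, counting C1D1 as day 1.

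**1. Marrow collected against marrow assigned**

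| Marrow | Nominal time | T-cell tubes (11.11.2) | Assigned to these assays (11.11.6) |
|---|---|---|---|
| Baseline | before first vaccine | yes | yes |
| End of cycle 1 | about day 29 | yes | no |
| C5D1 | day 113 | yes | no |
| C9D1, C13D1 and so on | every 112 days | yes | no |
| End of treatment | near day 29 of last decitabine cycle | yes | yes, taking this as the off-study sample |

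**2. C5D1 relative to the vaccine series.** Section 10.1 gives vaccine on day -14 and on day 15 of cycles 1 to 4.
- Fifth vaccine: 3 × 28 + 15 = day 99.
- C5D1: 4 × 28 + 1 = day 113.
- Nominal gap: 113 − 99 = 14 days.
- Section 11.11.2 allows ±14 days for this marrow, so the gap runs from 0 to 28 days from that window alone. The ±7 day treatment window (10.1) and permitted delays (10.1.3) widen it further.

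**3. Off-study marrow.** Assumption: the 18 to 24 month median in Section 7 stands for time off study.
- 18 months: 18 × 365.25 / 12 = 547.9 days; 547.9 / 28 = 19.6 cycles.
- 24 months: 730.5 days; 730.5 / 28 = 26.1 cycles.
- After the fifth vaccine: (547.9 − 99) / 28 = 16.0 cycles and (730.5 − 99) / 28 = 22.6 cycles.

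**4. On-treatment marrows scheduled by then.**
- By 18 months: end of cycle 1, C5D1, C9D1, C13D1 and C17D1 (day 16 × 28 + 1 = 449), so 5.
- By 24 months: also C21D1 (day 561) and C25D1 (day 673), so 7.
- None is assigned to either assay.

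**5. Exposure to the combination.** Dropping nivolumab or vaccine by choice is allowed only after cycle 8, and C5D1 precedes that. A patient who dropped both straight after cycle 8 would have had 19.6 − 8 = 11.6 to 26.1 − 8 = 18.1 cycles of decitabine alone by the assumed median off-study time.

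**6. Interim looks.** Section 7 plans correlative analyses after every 3 patients have been treated for 5 months or have stopped. Five months is 5 × 365.25 / 12 = 152 days. On schedule the C5D1 marrow exists by day 113, or day 127 at the end of its window. A patient still on treatment has no off-study marrow by then.

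**The case against.** **Marrow T cells are supplementary.** In Section 8.2 the NY-ESO-1 antibody and T-cell endpoint does not name marrow, and Section 11.11.6 rests immunogenicity on the serial samples and adds marrow to the blood studies. This stands and limits the size of the point: a vaccine response in blood would not be missed because of marrow timing.

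**Off-study marrow can still fall during combination therapy.** Section 10.1 continues boosters indefinitely, and nivolumab until progression or patient choice. Section 11.8 places the end-of-treatment visit near day 29 of the last decitabine cycle, before any further therapy. This stands for patients who dropped nothing. A reader might infer that the post sample always comes after the combination has stopped; the documents do not support that. The outcome-dependent timing remains for everyone.

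**The plan may intend to assay the on-treatment marrow.** The T-cell label in Section 11.11.2 could be read that way. But Section 11.11.6 lists two time points and no section adds another, so the two need reconciling on either reading.

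**C5D1 is itself selective.** It exists only for patients who complete about four cycles; in the predecessor trial 2 of 9 did not, because of serious adverse events (Section 2.2). This stands in part. Section 9.2 replaces expansion patients who leave before the end of cycle 4 for reasons unrelated to toxicity, so most should reach it.

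**Conclusion.** The point holds in a limited form. Section 11.11.6 gives the two marrow assays no on-treatment sample, although suitable marrow is collected, and the sample it does name comes at a time that varies with outcome. The assumed median is about cycle 20 to 26, against about day 113 for C5D1. That range treats median progression-free survival as time off study; exits for toxicity, transplant, delay or withdrawal would shorten it. The consequence is confined to the supplementary marrow part of the immune assessment.

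Four stronger readings are tempting but unsupported:
- That off-study marrow is the post value in the Wilcoxon signed-rank test. Section 19.4 does not say so, and it refers to measurements during treatment.
- That C5D1 falls at the same time for every patient. The windows and permitted delays make it near a common time, not identical.
- That patients who stay on treatment never contribute a pair. Section 8.3 plans a marrow at end of study, and Section 7 limits time on study.
- That the marrow mass cytometry is also confined to off-study samples. Section 8.2 says only "To evaluate the Immune cell profile in the peripheral blood and bone marrow following combination therapy using mass cytometry" and gives no sampling times.

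**What to change.** Reconcile Section 11.11.6 with Section 11.11.2:
- Name the already-collected C5D1 marrow as the designated on-treatment post sample for the NY-ESO-1 T-cell assay and for the CD4+/CD8+/FOXP3+/CD19+ flow.
- For patients who leave before C5D1, use the last earlier on-treatment marrow and flag it. This will normally be the end-of-cycle-1 sample, which may be a biopsy where an aspirate could not be obtained.
- Keep the off-study marrow, reported separately as a descriptive end-of-treatment time point.
- For the marrow mass cytometry in Section 8.2, stating C5D1 would be a clarification only.

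The cost is a short protocol edit and one added assay run per patient on banked marrow, with no new procedure. The limitation is that C5D1 is available only for patients who complete about four cycles.

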11.11.7 Dendritic Cell Function

In the event that we do not observe antigen specific immune responses, this could reflect APC dysfunction related either to the underlying malignancy, or to treatment with decitabine. The function of APCs in MDS has not been tested, thus we will determine whether cultured APCs from our enrolled MDS patients are able to effectively process and present antigen in order to activate T-cells. Exposure to decitabine has been previously shown to enhance the development and maturation of APCs in solid tumor models (64), as well as to enhance immune recognition in other hematological malignancies (65). We will examine APC function at baseline and following 2 and 4 cycles of decitabine treatment (3 time points). For these assays, blood samples will be obtained and cultured under conditions known to induce APC differentiation (66, 67). The ability of these cells to activate NY-ESO-1 specific T-cells derived from either autologous peripheral blood mononuclear cells or from ovarian cancer patients with NY-ESO-1 expressing tumors, (depending upon the HLA type of the patient) will be determined by the ELISPOT technique for IFN γ , as above. We will also assess the ability of these cells to induce an allo-reactive T-cell response from

PROTOCOL TITLE: I 49217 - Phase 1 CDX-1401/ Poly-ICLC +Decitabine +Nivolumab in Patients with MDS or Low Blast Count AML

healthy donor T-cells. These assays will test the function of APCs in MDS patients and determine if exposure to decitabine has an effect upon this function.

The induction of antitumor T-cell responses associated with IFN γ production are believed to be critical to the effects of cancer vaccination in solid tumors, however such responses are limited by the action of immunosuppressive Tregs which allow escape by malignant cells (59, 60, 68). Recently Tregs have been demonstrated to be complex, differentiating and migrating in response to signals from the immune system (60). Specific subsets of Tregs have been demonstrated to have differential suppressive effects upon anti-tumor immune responsiveness (60, 69). One study in MDS and AML patients treated with azacitidine following BMT suggests that HMAs alter Treg function by promoting graft versus leukemia effects over graft versus host effects, while another has demonstrated enhanced immuno-suppressive effects (49, 68). In order to determine if MDS patients undergoing therapy with CDX-1401/poly ICLC decitabine and nivolumab demonstrate changes in Treg differentiation favoring anti-tumor immune responsiveness over immune suppression, we will analyze Tregs sampled serially for changes in the expression of markers (including CD127, CD45RA, CXCR3 and Helios) associated with Treg biological function using flow cytometry (56, 59, 70, 71). Significant changes in Treg subsets with therapy would suggest that decitabine can alter the immune milieu in patients with MDS.

The methods to analyze the T cell response to cancer antigens used in this study are well established. However, as T cell biology and immune regulation are very active fields of discovery, the opportunity exists to refine and extend the analysis of the T cell response. Therefore, although most of the blood drawn for the analysis of the immune response will be used for the assays listed in this section, a small part may be used to explore other aspects of the T cell response using novel techniques such as time of flight cytometry. This work may also involve establishing T cell lines and clones in culture, and collaborations with investigators outside of Roswell Park Cancer Institute. As these exploratory approaches, by definition, have not yet been validated, the results will not be endpoints in the evaluation of the current study.

